#### **3.3.2.6 Pre-specified Subgroup Analysis**

If more than one PVAC catheter model (PVAC or PVAC GOLD) is used during the VICTORY AF study a subgroup analysis will be performed to assess the 6-month post-procedural effectiveness by PVAC catheter subgroup as described in section 3.1.3.3.

### **3.3.3 Secondary Objective #3: Pulmonary Vein Stenosis**

Characterize the incidence of PVS 3 months post ablation procedure as determined by MRI or CT scan.

#### **3.3.3.1 Hypothesis**

There is no pre-specified hypothesis associated with this secondary objective.

#### **3.3.3.2 Definition of Pulmonary Vein Stenosis**

Pulmonary vein stenosis is defined as a greater than 70% reduction in the baseline luminal diameter occurring in any one or more of the pulmonary veins.

Specifically, a subject with an ablation attempt where at least one Phased RF catheter was deployed in the left atrium (i.e. placed in left atrium with Phased RF energy delivered) will be considered PVS positive if they have a greater than 70% reduction from baseline in either the major axis diameter or the minor axis diameter in any of the six pulmonary veins (right superior, right inferior, right middle, left superior, left inferior, or left common).

---

### 3.3.3.3 Analysis Methods

One hundred (100) subjects will be randomized to the PVS assessment cohort. Subjects randomized to the PVS assessment cohort will have a CT-scan or MRI scan at their baseline visit and a CT-scan or MRI scan for PVS assessment at their first 3-month post-ablation visit (e.g. subjects with a reablation procedure following their 3-month post index ablation assessment will not have another scan at their 3-month post reablation visit). The CT/MRI core laboratory will record the major and minor axis diameter in mm of each pulmonary vein at the baseline and 3-month post-ablation visit. For each pulmonary vein and axis, the change in pulmonary vein diameter will be calculated as:  $((3\text{-month post-ablation diameter minus baseline diameter})/\text{baseline diameter}) \times 100\%$ . If this value is less than or equal to negative 70% for either the major or minor axis on any of the six pulmonary veins, the subject will be considered PVS positive. For computing the PVS rate at 3 months post ablation, the denominator will be all subjects that are randomized to the PVS assessment cohort, have at least one ablation procedure with one or more Phased RF catheters deployed in the left atrium with Phased RF energy delivered, and either have evaluable CT or MRI scans available at their baseline and 3-month follow up visits for at least four of the six pulmonary veins or meet the definition of PVS positive on at least one axis of one of the six pulmonary veins. The numerator will be all subjects included in the denominator that meet the definition of PVS on at least one axis of one of the six pulmonary veins. A two-sided 95% exact confidence interval for the 3-month post-procedure PVS rate will be calculated. SAS code similar to the PROC FREQ statements in section 3.3.1.3 will be used to compute the two-sided 95% exact confidence interval for the PVS rate.

Additionally, descriptive statistics and/or graphical methods will be used to summarize the major and minor diameter at baseline and 3-months post-ablation as well as percent change in diameter for each pulmonary vein.

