12.3.3.4 Analysis Methods

One hundred (100) subjects will be randomized to the PVS assessment cohort. Subjects randomized to the PVS assessment cohort will have a CT-scan or MRI scan at their baseline visit and a CT-scan or MRI scan for PVS assessment at their first 3-month post-ablation visit (e.g. subjects with a reablation procedure following their 3-month post index ablation assessment will not have another scan at their 3-month post reablation visit). The core laboratory's assessment of PVS status will be collected on the CRFs. For computing the PVS rate at 3 months post ablation the denominator will be all subjects that are randomized to the PVS assessment cohort, have at least one ablation procedure with one or more Phased RF catheters deployed, and have evaluable CT or MRI scans available at their baseline and 3-month follow up visits. The numerator will be all subjects included in the denominator that were classified by the core laboratory as having PVS by the core laboratory. A two-sided 95% exact confidence interval for the 3-month post-procedure PVS rate will be calculated.

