### 3.3.3.4 Determination of Subjects for Analysis

Only those subjects that are randomized to the PVS assessment cohort, have at least one ablation procedure with one or more Phased RF catheters deployed in the left atrium with Phased RF energy delivered, and have CT or MRI scans at baseline and at the 3-month follow-up visit (or 3-month post-reablation visit if subject was reablated and reablation occurred prior to the 3-month post index ablation visit) that are readable by the core lab for at least four of the six pulmonary veins or have a greater than 70% reduction in vein diameter in one or more veins will be included in the analysis of this objective.

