### 3.3.3.5 Confidence Interval Width

The PVS rate among all 176 ablated subjects in the TTOP-AF study was 4% (7/176; 95% CI: 1.6% to 8%). Based on the added training and other mitigation strategies employed in this protocol to avoid PVS, it is assumed that the true PVS rate will be 2%. If at least 80 of the 100 subjects randomized to the PVS assessment cohort have readable baseline and 3-month follow-up MRI or CT scans and the true PVS rate is 2%, the exact 95% two-sided confidence interval should have a width no larger than 7.8% with an upper confidence boundary no greater than 8%.

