### 3.3.3.6 Missing data

Subjects missing a readable baseline or 3-month follow-up MRI or CT-scan in more than two pulmonary veins will not be included in the main analysis cohort for this objective unless they are PVS positive in one of their observed pulmonary veins. However, should the issue of missing data arise; all subjects randomized to the PVS assessment cohort

[REDACTED]

[REDACTED]

[REDACTED]

[REDACTED]

[REDACTED]

[REDACTED]

[REDACTED]

[REDACTED]

[REDACTED]

[REDACTED]

[REDACTED]

[figure not shown]
[REDACTED]

[REDACTED]

[REDACTED]

[REDACTED]

[REDACTED]

[REDACTED]

[REDACTED]  
[REDACTED]  
[REDACTED]  
[REDACTED]

[REDACTED]

[REDACTED]  
[REDACTED]

[REDACTED]  
[REDACTED]

[REDACTED]  
[REDACTED]  
[REDACTED]  
[REDACTED]

[REDACTED]  
[REDACTED]  
[REDACTED]  
[REDACTED]  
[REDACTED]  
[REDACTED]  
[REDACTED]  
[REDACTED]  
[REDACTED]

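### The SAP judges PVS evaluability against a fixed list of six veins, so a fully imaged subject with a left common vein and no right middle vein may enter only if PVS positive

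*SAP*

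**What the plan says.** SAP 3.3.3.2 makes PVS an any-vein outcome: a subject is positive on a sufficient diameter loss "in any of the six pulmonary veins (right superior, right inferior, right middle, left superior, left inferior, or left common").

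Three SAP sections then decide who is analysed:

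- Section 3.3.3.3 (denominator) requires evaluable baseline and 3-month scans "for at least four of the six pulmonary veins or meet the definition of PVS positive"; a single axis of a single vein suffices for the second route.
- Section 3.3.3.4 (analysis set) requires scans "readable by the core lab for at least four of the six pulmonary veins or have a greater than 70% reduction in vein diameter". Again a single such vein is enough.
- Section 3.3.3.6 (missing data) works from the other side. Subjects with no usable image "in more than two pulmonary veins will not be included in the main analysis cohort for this objective unless they are PVS positive".

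Protocol 12.3.3.4 asks only that subjects "have evaluable CT or MRI scans available at their baseline and 3-month follow up visits". Neither that section nor Protocol 12.3.3.5 sets a vein count or lets a subject in because of a positive result. Both features are new in the SAP.

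The objective has no hypothesis (SAP 3.3.3.1). The precision statement in SAP 3.3.3.5 takes a true rate of 2% and at least 80 readable subjects out of 100 randomised.

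**The concern.** Two features combine. First, the threshold of four is set against six named veins, and the list includes the left common vein alongside the left superior and left inferior. If the left common vein is recorded instead of those two, no subject has all six, and some subjects fall below four through anatomy alone. Second, a subject below the threshold is readmitted only if PVS positive, so inclusion depends on the outcome.

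A negative subject with an unread vein is truly undetermined, and leaving that subject out can be defended. A subject whose existing veins were all read and all negative is fully determined, yet the literal rule discards that subject and keeps the same subject with a stenosis.

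PVS was one of the two safety concerns behind the advisory panel's vote (SAP 2.3), and SAP 3.3.3.5 sets out the 4% rate (7/176) from the sponsor's earlier trial. The cohort is small, so the rule for who counts should not depend on the result.

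**Working it through.** **1. The plan's own precision figure.** Inputs from SAP 3.3.3.5: n = 80, rate 2%, exact two-sided 95% interval. The expected count is 0.02 × 80 = 1.6. Clopper-Pearson limits from beta quantiles at x = 1.6 are 0.16% and 7.97%, a width of 7.81 points. This matches the stated 7.8% and 8%. With whole counts, 1/80 gives 0.03% to 6.77% and 2/80 gives 0.30% to 8.74%, so one event moves the upper limit by about 2 points.

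**2. Listed veins by anatomy.** The six come from SAP 3.3.3.2. Rows 3 and 4 assume that a left common vein is recorded in place of the two left veins; the SAP does not state this.

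| Anatomy | Listed veins | Entry if every vein is read and negative |
|---|---|---|
| Four separate veins | 4 | Yes, none to spare |
| Four veins plus right middle | 5 | Yes |
| Left common, no right middle | 2 right + 1 = 3 | No; only if PVS positive |
| Left common plus right middle | 3 right + 1 = 4 | Yes, none to spare |
| Left common with both left branches also measured, no right middle | 5 | Yes |

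Only row 3 is shut out by anatomy.

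**3. The three sections on row 3.** Under 3.3.3.3 and 3.3.3.4 the subject has three readable veins, fewer than four, and is out if negative. Under 3.3.3.6 the answer depends on whether an absent vein is a missing reading. If it is, 6 − 3 = 3 are missing, more than two, and the subject is out. If it is not, none is missing and 3.3.3.6 does not exclude the subject, which conflicts with the other two sections.

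**4. Direction.** Positives stay in under either rule, so the numerator is unchanged. The literal rule removes only negatives, so the denominator shrinks. The estimate can therefore only rise and the evaluable number can only fall, whatever the PVS risk in each anatomy.

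**5. Size.** Let p be the true rate and f the share of subjects in row 3. That is f = (share with a left common vein) × (share of those without a right middle vein). The documents give neither factor, so f is assumed. Take PVS risk as equal across anatomies and all present veins as readable.

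- Share retained = p + (1 − p)(1 − f) = 1 − f(1 − p)
- Expected rate, approximately = p / [1 − f(1 − p)]

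| f (assumed) | Share retained at p = 2% | Rate | Left of 80 | Left of 100 |
|---|---|---|---|---|
| 5% | 1 − 0.05 × 0.98 = 0.951 | 2.10% | 76.1 | 95.1 |
| 10% | 1 − 0.10 × 0.98 = 0.902 | 2.22% | 72.2 | 90.2 |
| 20% | 1 − 0.20 × 0.98 = 0.804 | 2.49% | 64.3 | 80.4 |

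Wider assumptions of f = 2.5% and f = 30% give 2.05% and 2.83%. At a true 4%, f = 5% and 20% give 0.04/0.952 = 4.20% and 0.04/0.808 = 4.95%.

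**6. Precision.** By the method of step 1 at a 2% rate, the interval width is 7.8 points at n = 80, 8.1 at 76, 8.4 at 72 and 9.0 at 64.

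**The case against.** The strongest reply is that the SAP never says a left common vein removes the left superior and left inferior from measurement. Section 3.3.3.3 has the core laboratory record every vein. If the branches beyond a common trunk are measured too, the subject has five listed veins and the anatomical problem disappears. This stands, and it is why the point is conditional. The text still does not settle it.

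A second reply is that, for an any-vein outcome, one stenosed vein settles the subject's status while an unread vein leaves a negative open. On that view, keeping positives and withholding incomplete negatives is a reasonable safety convention, and it also covers the four-vein subject with one unreadable vein. This stands for incomplete imaging. It does not reach a negative subject with nothing left unread.

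Third, the effect is small and runs against the device, and Protocol 12.3.3.7 plans a tipping point analysis that starts non-evaluable subjects as PVS negative. That is partial cover. Its first step would restore the discarded negatives, but later steps would turn known negatives into positives, and the main estimate would be unchanged. The matching SAP text in 3.3.3.6 is redacted after its opening words, so nothing is inferred from it.

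A reader might infer that every subject with a left common vein enters only if positive. The documents do not support that, because those with a right middle vein have four listed veins and enter normally if all four are readable. A reader might also subtract the losses from 80 and quote 1/80 against 1/64, with upper limits of 6.8% and 8.4%. But the 80 already allows for 20 losses out of 100. If 20% of the 100 were affected and nothing else were lost, 80.4 would remain, which is the planned number.

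**Conclusion.** The point holds in a limited form. On the face of the SAP, a fixed count of four out of six decides evaluability, and subjects below it are readmitted only by a positive result. If a left common vein replaces the two left veins in the record, a fully imaged negative subject with a left common vein and no right middle vein is dropped. The direction is certain: a higher rate and fewer subjects.

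The size rests on an affected share that the documents do not give and on equal PVS risk across anatomies. For an assumed share of 5% to 20%, the shift at a true 2% is 0.1 to 0.5 percentage points, against a planned interval about 7.8 points wide. The objective is descriptive and no success decision changes. A claim of material bias, or of a cohort cut well below plan, would go beyond the documents. The case for a change rests on clear pre-specification at low cost.

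**What to change.** In SAP 3.3.3.3, 3.3.3.4 and 3.3.3.6, replace the count out of six with one rule tied to the veins present on the subject's own baseline scan:

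- A subject whose present veins are all readable at both scans is evaluable, whatever the result. If some unreadable veins are to be tolerated, state the number relative to the veins present.
- An anatomically absent vein is not a missing vein. State whether the left superior and left inferior branches are measured when a left common vein is recorded.
- PVS-positive subjects with incomplete imaging stay in the main estimate, so no observed stenosis leaves it. Also report the rate without subjects who enter only by being positive.

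Use the same wording in all three sections and note the departure from the denominator in Protocol 12.3.3.4 and 12.3.3.5. The cost is SAP wording and one extra tabulation. The core laboratory already records diameters vein by vein, so no new imaging or reading is needed.

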### 3.3.3.4 Determination of Subjects for Analysis

Only those subjects that are randomized to the PVS assessment cohort, have at least one ablation procedure with one or more Phased RF catheters deployed in the left atrium with Phased RF energy delivered, and have CT or MRI scans at baseline and at the 3-month follow-up visit (or 3-month post-reablation visit if subject was reablated and reablation occurred prior to the 3-month post index ablation visit) that are readable by the core lab for at least four of the six pulmonary veins or have a greater than 70% reduction in vein diameter in one or more veins will be included in the analysis of this objective.

### 3.3.3.5 Confidence Interval Width

The PVS rate among all 176 ablated subjects in the TTOP-AF study was 4% (7/176; 95% CI: 1.6% to 8%). Based on the added training and other mitigation strategies employed in this protocol to avoid PVS, it is assumed that the true PVS rate will be 2%. If at least 80 of the 100 subjects randomized to the PVS assessment cohort have readable baseline and 3-month follow-up MRI or CT scans and the true PVS rate is 2%, the exact 95% two-sided confidence interval should have a width no larger than 7.8% with an upper confidence boundary no greater than 8%.

### 3.3.3.6 Missing data

Subjects missing a readable baseline or 3-month follow-up MRI or CT-scan in more than two pulmonary veins will not be included in the main analysis cohort for this objective unless they are PVS positive in one of their observed pulmonary veins. However, should the issue of missing data arise; all subjects randomized to the PVS assessment cohort

[REDACTED]

[REDACTED]

[REDACTED]

[REDACTED]

[REDACTED]

[REDACTED]

[REDACTED]

[REDACTED]

[REDACTED]

[REDACTED]

[REDACTED]

[figure not shown]
[REDACTED]

[REDACTED]

[REDACTED]

[REDACTED]

[REDACTED]

[REDACTED]

[REDACTED]  
[REDACTED]  
[REDACTED]  
[REDACTED]

[REDACTED]

[REDACTED]  
[REDACTED]

[REDACTED]  
[REDACTED]

[REDACTED]  
[REDACTED]  
[REDACTED]  
[REDACTED]

[REDACTED]  
[REDACTED]  
[REDACTED]  
[REDACTED]  
[REDACTED]  
[REDACTED]  
[REDACTED]  
[REDACTED]  
[REDACTED]
